5 EFFECTIVENESS ANALYSIS STRATEGY

EFFECTIVENESS ENDPOINTS

5.1.1 Primary Effectiveness Endpoint

The primary effectiveness endpoint is measured using the mean Binocular BCDVA (at 4 m) at Visit 1 (3-5 years postoperative, +/- 90 days).

5.2 EFFECTIVENESS HYPOTHESES

No hypothesis testing is planned.

5.3 STATISTICAL METHODS FOR EFFECTIVENESS ANALYSIS

Except otherwise stated, the analysis set for all effectiveness analyses is the FAS as defined in Section 2.1. In the event there is a 10% exclusion in subjects when comparing the FAS and BAS populations, effectiveness analysis tables will be presented for both the FAS and BAS, if requested.

Performance outcome measures will be stratified by the subgroups defined in section 10.4.

5.3.1 Primary Effectiveness Analysis

5.3.1.1 *Mean Binocular Best Corrected Distance Visual Acuity (BCDVA)*

Mean binocular BCDVA is performed for distance visual acuity (VA) at the retrospective postoperative visit (1 to 6 months) and at prospective Visit 1 using ETDRS charts validated for testing at 4 m for logarithm of the minimum angle of resolution (LogMAR) chart. The primary effectiveness endpoint, binocular BCDVA, will be summarized descriptively as a continuous variable (n, mean, median, standard deviation, minimum and maximum, and two-sided 95% CI for the mean) prospectively at Visit 1. The number and percentage of subjects in each of the following visual acuity categories will also be presented in the table:

Snellen categories:

- 20/20 or better (≤ 0.04 LogMAR)
- 20/25 or better (≤ 0.14 LogMAR)

[figure not shown]
- 20/32 or better (≤ 0.24 LogMAR)
- 20/40 or better (≤ 0.34 LogMAR)
- Worse than 20/40 (> 0.34 LogMAR)

[figure not shown]
The table will also be output for the retrospective postoperative visit (1 to 6 months post-op).

A listing for binocular BCDVA for patients with a 0.20 LogMAR or higher/worse will be output and includes the following variables: subject, age, sex, study device, lens model (OD/OS), visit, days from surgery, whether surgery was done due to refractive lens exchange (OD and OS, separately), BCDVA (converted to LogMAR), and Snellen Category. All visits for patients meeting the criteria will be included in listing to provide a comprehensive picture of the subject's visual acuity over the duration of the study. Snellen categories for the listing will be as follows:

- ≤ -0.14 LogMAR = "Better than 20/16"
- < -0.14 to -0.04 LogMAR = "~20/16"
- < -0.04 to 0.04 LogMAR = "~20/20"
- < 0.04 to 0.14 LogMAR = "~20/25"
- < 0.14 to 0.24 LogMAR = "~20/32"
- < 0.24 to 0.34 LogMAR = "~20/40"
- < 0.34 to 0.44 LogMAR = "~20/50"
- < 0.44 to 0.51 LogMAR = "~20/60"
- < 0.51 to 0.57 LogMAR = "~20/70"
- < 0.57 to 0.65 LogMAR = "~20/80"
- < 0.65 to 0.74 LogMAR = "~20/100"
- < 0.74 to 0.80 LogMAR = "~20/120"
- < 0.80 to 0.85 LogMAR = "~20/130"
- < 0.85 to 0.90 LogMAR = "~20/150"
- < 0.90 to 0.96 LogMAR = "~20/170"
- < 0.96 to 1.05 LogMAR = "~20/200"
- < 1.05 to 1.14 LogMAR = "~20/250"
- < 1.14 to 1.24 LogMAR = "~20/300"
- < 1.24 to 1.35 LogMAR = "~20/400"
- < 1.35 to 1.46 LogMAR = "~20/500"
- < 1.46 to 1.56 LogMAR = "~20/650"
- < 1.56 to 1.65 LogMAR = "~20/800"
- < 1.65 to 1.75 LogMAR = "~20/1000"
- < 1.75 to 1.85 LogMAR = "~20/1250"
- < 1.85 to 1.95 LogMAR = "~20/1600"
- < 1.95 to 2.05 LogMAR = "~20/2000"
- > 2.05 LogMAR = "Worse than 20/2000"

6.2 SAFETY HYPOTHESES

There are no formal safety hypotheses in this study.

6.3 STATISTICAL METHODS FOR SAFETY ANALYSIS

The focus of the safety analysis will be to conduct a comprehensive descriptive assessment of AEs and other listed parameters in the safety analysis set and provide listings if necessary. Except otherwise stated, the analysis set for all safety analyses is the FAS as defined in Section 2.1. For this study, AEs from time of exposure to the study model IOL to the prospective study visit are considered.

All safety outcome measures will be stratified by the subgroups defined in section 10.4.

While imputation is not defined for this study, adverse events with partial AE dates will be considered for analysis if the AE occurs within the same month of implantation or if the AE can be determined as occurring after implantation using the partial date.

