6.3 Evaluation Criteria / Effectiveness and Safety

The endpoints chosen align with those identified in the AcrySof IQ PanOptix Trifocal Intraocular Lenses State of the Art [REDACTED] Study assessments will be described in Section 7.3. Retrospective data will be collected from the pre-operative and surgical visits and any safety outcomes reported prior to enrollment. Prospective data will be collected at study enrollment 3 to 5 years (+/- 90 days) after IOL implantation.

6.3.1 *Primary Clinical Endpoint*

[figure not shown]

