7.3 Prospective Clinical Procedures and Assessments

After obtaining informed consent and confirming eligibility, assessments will be conducted for the enrolled subject as described in the sections below. Retrospective data will be collected regarding the pre-operative, operative, and post-operative activities. All assessments and data collection are described in the sections below.

7.3.1 *Demographics*

The Investigator or designee will verify that all required demographic details have been documented for each subject enrolled, including age, race, ethnicity, and sex.

7.3.2 *Eligibility*

Verify that all inclusion criteria listed in Section 6.4.4 are fulfilled by the subject, and that none of the exclusion criteria listed in Section 6.4.5 apply.

7.3.3 *Medical History and Concomitant Medications*

Document concomitant medications (taken within the past 30 days prior to the date of surgery) and Medical History (within 30 days prior to the date of surgery) in the subject source documents (i.e., subject's chart).

Any medical condition that has a start date preceding surgery and implantation of the study model IOLs (surgery date) will be captured as medical history. Any medical condition that started from/after surgery and implantation of the study model IOLs should be captured as AEs. For subjects with history of IOL exchange, information regarding explanted IOL model and reason for explantation should be extracted from chart review (if available) and recorded as medical history.

In the electronic data capture (EDC) system, only limited information regarding concomitant medications and medical history will be captured, as noted below.

- Medical History: Document all ocular history and targeted systemic history. In the EDC, there is a prepopulated dropdown field with items of interest that is consistent with Table 2.
- Concomitant medications: Document all ocular medications (excluding routine cataract surgical medications) and targeted systemic medications used to treat conditions documented in Medical History and AEs.

Table 2. Targeted Medical History

Diabetes	Sarcoidosis	Sjogren's Syndrome	Autoimmune Disorder
Multiple Sclerosis	Hypertension	Grave's Disease	Sickle Cell Disease
Atherosclerosis	HIV Infection	Rheumatoid Arthritis	

7.3.4 *Manifest Refraction*

MRSE will be assessed prospectively and retrospectively from the preoperative assessment. Reference Attachment 17.2.3 for further details on prospective manifest refraction procedures.

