- Clinically Significant Requiring YAG: Clinically significant PCO adversely affecting subject's VA and requiring posterior capsulotomy.

For posterior capsulotomy assessment, indicate whether a posterior capsulotomy has been performed. If performed, report the date of the procedure.

If subjective PCO is graded as present, also record whether it is due to residual cataract (e.g., posterior subcapsular cataract).

7.3.13 *Tonometry*

Perform tonometry assessment in both eyes according to the Investigator's standard of care. Record IOP.

7.3.14 *Dilated Fundus Examination*

Dilated fundus examination includes ophthalmoscopic assessments of the vitreous, retina, macula, choroid, and optic nerve of both eyes. This assessment must be performed by medically qualified study staff.

7.3.15 *Actual Axis of IOL Orientation*

Post-operatively, examine each toric IOL via slit lamp subjectively and document the actual IOL orientation in degrees (0-180 degrees) of the IOL axis (designated by the 3 indentions on each side of the toric IOL optic). It is recommended that a slit lamp photograph be printed and kept in the source. Actual axis of orientation should be completed after dilation.

Post-operative Day 1 IOL orientation in degrees (0-180 degrees) of the IOL axis will be extracted from the chart review, if available.

7.3.18 *Adverse Events*

AEs are collected from the time of initial exposure to the study model IOL(s) and throughout the duration of the study. Any preexisting medical conditions or signs/symptoms present in a subject prior to exposure of the study model IOL(s) (i.e., before cataract surgery) are not considered AEs in the study and should be recorded in the Medical History section of the eCRF. See Section 9.2 and 9.3 for further details.

7.3.19 *Device Deficiencies*

Record any Device Deficiencies that are reported or observed since the time of initial exposure to the study model IOL(s). Requirements for reporting device deficiencies in the study can be found in Section 9.

7.4 *Retrospective Data Collection*

If available, retrospective data will be collected regarding the pre-operative, operative, and post-operative activities, as detailed in the sections below.

7.4.1 *Biometry and Keratometry*

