10.3 MISSING DATA

No missing data imputation is planned for this study.

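### By implication, the partial-date rule in SAP 6.3 leaves out adverse events dated only with the implant year, a one-directional loss confined to the first 12 months after surgery

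*SAP*

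**What the plan says.** SAP 6.3 sets the safety window: "AEs from time of exposure to the study model IOL to the prospective study visit are considered". For incomplete dates it gives two alternative conditions. First, "adverse events with partial AE dates will be considered for analysis if the AE occurs within the same month of implantation". Second, "or if the AE can be determined as occurring after implantation using the partial date". SAP 10.3 adds: "No missing data imputation is planned for this study".

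The protocol separates pre-implant from post-implant conditions when the data are entered. Section 7.3.18 says "AEs are collected from the time of initial exposure to the study model IOL(s) and throughout the duration of the study", and that conditions present before exposure "are not considered AEs in the study and should be recorded in the Medical History section of the eCRF". Section 9.3 repeats this. Section 7.3.3 gives the other half of the split: "Any medical condition that started from/after surgery and implantation of the study model IOLs should be captured as AEs".

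Under protocol 6.3.1.2 the primary safety endpoint covers all adverse events, drawn from both Visit 1 and the retrospective data. On timing, protocol 6.3 says: "Prospective data will be collected at study enrollment 3 to 5 years (+/- 90 days) after IOL implantation".

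**The concern.** The SAP asks the date to prove something the investigator has already decided. An entry on the AE form has been judged to start at or after exposure. If its date is only a year, and that year is the implant year, the date cannot prove this again, and the rule offers no other way in.

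The first condition already gives the benefit of the doubt at month level: an event dated to the implant month is kept although its day might precede surgery. The rule gives no such benefit at year level.

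The events at risk are those soonest after surgery, and the error runs one way, because omission can only lower a reported rate. Incomplete dates are plausible here, since events are abstracted from charts and asked about at a single visit years after surgery; the sponsor wrote a rule for them. Protocol 6.4.1 intends the descriptive results to be compared with State of the Art safety thresholds. With 100 evaluable subjects planned per group, one subject lost from a subject-level table moves the rate by 1/100 = 1.0 percentage point.

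**Working it through.** The plan gives no figure on this point, so there is none to reproduce.

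**Step 1. Apply the two conditions to each kind of partial date.** Illustrative implant date: 15 June 2021.

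| Recorded AE date | Same month as implant? | Shown to be after implant? | Result |
|---|---|---|---|
| June 2021 | yes | not needed | kept |
| July 2021 | no | yes | kept |
| May 2021 | no | no (before) | left out |
| 2022 or 2024, year only | no | yes | kept |
| 2021, year only | cannot be shown | cannot be shown | left out by implication |

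Only the last row is a problem. January implants are an arguable exception: any month of the implant year is then either the implant month or later, so a year-only date satisfies one condition or the other.

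**Step 2. Chance that a year-only post-implant event is lost, by onset time.** Assumption (not in the documents): implant dates are uniform over the calendar year. An event T months after surgery then falls in the implant year with probability 1 - T/12 for T up to 12, and 0 afterwards.

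- T = 1: 1 - 1/12 = 92%
- T = 3: 1 - 3/12 = 75%
- T = 6: 1 - 6/12 = 50%
- T = 9: 1 - 9/12 = 25%
- T = 12 or more: 0%

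**Step 3. Share of all year-only events lost over follow-up.** Further assumption: onset times are uniform over F years. The share is (1/F) × ∫ from 0 to 1 of (1 - t) dt = 0.5/F.

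- F = 3: 0.5/3 = 16.7%
- F = 4: 0.5/4 = 12.5%
- F = 5: 0.5/5 = 10.0%
- With the 90-day windows, about 2.75 to 5.25 years: 18.2% to 9.5%

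A simulation of 2,000,000 draws agreed. Half of the lost events lay within about 3.5 months of surgery, 75% within 6 months and all within 12. If January implants are treated as resolvable, the range for 5 to 3 years falls to about 8% to 14%.

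**Step 4. Sensitivity to early clustering.** Let a fraction f of events fall evenly in the first 3 months and the rest evenly from 3 months to F years. The average loss probability in the first 3 months is 1 - 1.5/12 = 0.875. For the rest it is (0.75²/2)/(F - 0.25) = 0.28125/(F - 0.25), which is 0.102 for F = 3 and 0.059 for F = 5. The share lost is 0.875f plus (1 - f) times that value.

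| f | F = 5 | F = 3 |
|---|---|---|
| 0.25 | 26% | 30% |
| 0.50 | 47% | 49% |
| 0.75 | 67% | 68% |

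**Step 5. Effect on the AE tables.** The loss as a share of all AEs is the share above times the fraction of AEs dated by year alone. That fraction is not given. If it were 5% (assumption), the loss would be 0.05 × 10% to 0.05 × 16.7%, or 0.5% to 0.8% of AEs, with even timing, and 0.05 × 68% = 3.4% in the most front-loaded case. If it were 20% (assumption), the figures would be 2.0% to 3.3%, and 13.6%.

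**The case against.** A reader might infer that every AE dated by year alone is dropped. The text does not support that: the second condition keeps a year-only event from any calendar year after the implant year, which covers most of the follow-up.

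A reader might also infer that events with no date at all are deleted. The sentence concerns partial dates; wholly missing dates are simply not addressed. That is a gap, not a deletion rule.

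The SAP says if, not only if, so exclusion is implied rather than stated. This objection stands as to wording, but a rule that excluded nothing would have no function, and two programmers could apply it differently.

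Nor does the rule remove only genuine post-implant events. It also screens out misfiled entries, such as a month and year before implantation. That use is legitimate and should be kept.

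The strongest objection concerns which events are exposed. Protocol 9.1 requires secondary surgical interventions, cystoid macular edema, endophthalmitis, retinal detachment and the other named events to be reported as serious. Protocol 9.3 requires a date of occurrence for serious events and adverse device effects, 10.3 requires missing data to be explained, and 11.3 provides for data clarification. An early lens repositioning is therefore less likely than a minor event to carry only a year. Protocol 9.3 also takes some expected early post-operative findings out of AE status. These points reduce the likely loss. They do not remove it: a required date need not be a complete one, and the remote monitoring in protocol 11.4 is limited to the regulatory binder, so monitors will not be recovering dates from charts.

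Finally, safety is descriptive with no formal hypotheses, so no test depends on the rule. That bears on severity, not on whether the rule is right.

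**Conclusion.** The concern holds for one category: an AE dated only with the implant calendar year, January implants arguably excepted. Read as written, and with no imputation, SAP 6.3 leaves such an event out although the protocol has already classed it as post-exposure. Every such loss lies within 12 months of surgery and can only lower reported AE rates.

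The size is conditional. The 1 - T/12 probabilities rest on uniform implant dates; the 10% to 17% share also assumes events spread evenly over 5 to 3 years, and it rises to about 26% to 68% if a quarter to three quarters of events fall in the first 3 months. All these are shares of year-only events, not of all AEs. The number of year-only dates is unknown, so the absolute effect may be small or nil.

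Two related gaps remain: wholly missing dates, and which eye's implantation is the reference when the two surgeries fall on different days.

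A reader might rate this as essential to correct before analysis. The unknown frequency, the descriptive analysis and the date requirement on the named serious events do not support that. It is a moderate point with a cheap remedy.

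**What to change.** Replace the partial-date sentence in SAP 6.3 with an include-by-default rule:

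> All events on the AE form are included unless the known date parts show onset before implantation of the affected eye (for non-ocular events, before first-eye implantation). Events with missing or ambiguous dates are included and flagged in the listing.

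This still removes entries whose date shows they were misfiled, settles wholly missing dates and names the reference eye. It is consistent with the no-imputation policy: for flagged events, days from surgery and duration are left blank where they cannot be calculated.

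The cost is one SAP sentence and a flag in the AE listing, with no new data collection. The downside is that a few pre-implant events may be counted, which is the conservative direction for a safety summary, and the flag lets a reader see how many events are affected.

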6.3.1 Primary Safety Endpoints

6.3.1.1 *Adverse Events Including Secondary Surgical Interventions*

Adverse Events

The following summary tables and listings will be provided:

1. All Adverse Events (for summary tables and tables by PT (ocular) or SOC/PT (non-ocular))
 - a. Ocular by Toricity (eye-level)
 - b. Non-ocular by Toricity (subject-level)
2. All Adverse Device Effects (tables by PT (ocular) or SOC/PT (non-ocular))
 - a. Ocular by Toricity (eye-level)
 - b. Non-ocular by Toricity (subject-level)
3. All Serious Adverse Events (including Serious Adverse Device Effects (SADEs)) (tables by PT (ocular) or SOC/PT (non-ocular))
 - a. Ocular by Toricity (eye-level)
 - b. Non-ocular by Toricity (subject-level)

4. Listing of all Adverse Events (listings by PT (ocular) or SOC/PT (non-ocular))
 - a. Non-serious Ocular (eye-level)
 - b. Non-serious Non-Ocular (subject-level)
 - c. Serious Ocular (eye-level)
 - d. Serious Non-ocular (subject-level)

Summary tables, by eye and event for ocular AEs and by subject for non-ocular AEs, will be output. For ocular AEs, the table will report the number of eyes experiencing an AE and the number of adverse events for all eyes by toricity and for non-ocular AEs, the table will include the number and percentage of subjects experiencing at least one AE by toricity. Both tables will include the number and percent of AEs related to study devices and/or procedures, and the seriousness criteria for serious AEs (per the CRF). For ocular AE summary tables, the AE event outcome and action taken due to the adverse event will also be reported.

In addition, the number and percentage of all AEs will be tabulated by Preferred Term (PT) for ocular AEs and by System Organ Class (SOC) and Preferred Term (PT) for non-ocular AEs using the Medical Dictionary for Regulatory Activities (MedDRA) dictionary (Version 26.1) for all subjects. If a subject has multiple AEs with the same PT, the PT will only be counted once per subject; similarly for subjects with multiple AEs per SOC, the SOC will only be counted once per subject. AEs will be sorted alphabetically by SOC and then by decreasing total frequency by PT.

Listings of AEs will include subject, age, sex, study device, lens model, implanted eye (first eye, second eye), eye (OD/OS), days from surgery, the MedDRA SOC and PT (for non-ocular listings) or PT (for ocular listings) for the AE, AE description, action taken, severity, causality, duration, and outcome, when available. Surgery eye will only be provided in listings of ocular AE. AEs related to the IOL are referred to as adverse device effects (ADE).

Pregnancy is not reportable as an AE; however, complications may be reportable and will be decided on a case-by-case basis.

Secondary Surgical Interventions (SSIs)

[figure not shown]
The number and percentage of eyes with secondary surgical interventions (SSIs), secondary surgical intervention type (exchange, removal, reposition), and secondary surgical intervention relationship (related to IOL, unrelated to IOL) will be presented separately for first implanted eye and second implanted eye (if applicable) and for all eyes by toricity.

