6.4.1 Sample Size

The study will recruit a total of 210 subjects for both AcrySof PanOptix IOL models to obtain 200 evaluable subjects (n=100 non-toric and n=100 toric). A minimum of 100 subjects bilaterally implanted with AcrySof PanOptix non-Toric should be evaluable. In addition, a minimum of 100 subjects with at least one eye implanted with AcrySof PanOptix Toric should be evaluable. Alcon will attempt to enroll all variants in the AcrySof PanOptix Toric family. ISO 22979 and ISO 11979-7 recommend a sample size of n=100 for IOLs where safety and performance risks can be adequately addressed with the sample size required of a Level B clinical investigation. Therefore, a target enrollment of up to 105 (enrolled) to achieve a goal of 100 evaluable subjects for both AcrySof PanOptix toric and non-toric models is justified by ISO standards for IOLs. Based on a pooled standard deviation of 0.07 logMAR and a t-distributed error, a sample size of 100 subjects gives an expected half width of a 95% confidence interval of 0.014 logMAR. Thus, it can be expected with 95% confidence that the estimated mean binocular BCDVA will be within 0.014 logMAR (< 1 letter on a logMAR visual acuity chart) of the true mean with a sample size of at least 100 subjects and a standard deviation of 0.07 logMAR. Descriptive results from this long-term RWE study are sufficient to provide a comparison to shorter term follow-up data of these models, and SotA safety and performance thresholds. Performance and safety outcome measures will be stratified by models (toric and non-toric).

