6.4.3 Prior and Concomitant Therapy or Medications

Due to the nature of the study, there are no protocol-specific exclusions, precautions, or guidance provided regarding the use of concomitant medications or therapies.

6.4.4 *Inclusion Criteria*

Subjects will be eligible to participate in the study if **all** of the following conditions exist:

1. Subjects must be 18 years old or older.
2. Subject or legally authorized representative must be able to understand and sign an IRB/IEC approved informed consent form (ICF).
3. Subject must have had bilateral implantation of AcrySof PanOptix or AcrySof PanOptix Toric models for 3 to 5 years prior to enrollment, including implantation up to 90 days before the 3-year timepoint and up to 90 days after the 5-year timepoint. A subject may have a Toric lens in one eye and a non-Toric in the fellow eye.
4. Subject must have a documented medical history and required pre-operative and operative information available for retrospective data collection.

6.4.5 *Exclusion Criteria*

Subjects will be excluded from participation in the study if **any** of the following conditions exist:

1. Subject is currently participating in another investigational drug or device study.
2. Subject has had corneal refractive surgery after of AcrySof PanOptix or AcrySof PanOptix Toric IOL implantation.
3. Subject exposed to a study IOL for a minimum of 3 years (-90 days) prior to Visit 1 that have subsequently undergone an IOL exchange and are no longer implanted with a study IOL at the time of enrollment.
4. Subject is pregnant or nursing at the time of enrollment.
5. Childbirth after IOL implantation.
6. Subject's retrospective data were not properly documented.

6.4.6 *Exit / Discontinuation Criteria*

Subjects will exit the study if **any** of the following conditions exist:

1. Subject voluntarily withdraws from the study.
2. Subject death.
3. Subject completes the protocol.
4. Subject is non-compliant with the protocol (as defined in Section 7.6)
5. Subject's well-being, in the opinion of the Investigator, would be compromised by study continuation.

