6.3.1.2 Device Deficiencies

The number and percentage of eyes with a device deficiency, each device deficiency description category (per CRF), and whether the device deficiency could have led to a serious adverse event will be reported separately for first implanted eye and second implanted eye (if applicable) and for all eyes by toricity. A device deficiencies listing will also be provided and includes the variables subject, age, sex, implanted eye (first eye, second eye), eye (OD/OS), study device, lens model,

days from surgery, the description of the deficiency, the circumstances that led to the device deficiency, whether the deficiency could have led to a SADE, and the medical term for the SADE.

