10.2 CONVENTIONS

Change in value from 1st visit to follow-up visit

For a given parameter, the change from baseline for postoperative visit, Visit X, will be calculated as:

Change: Follow-up Visit X - Baseline

Percent Change: $[(\text{Follow-up Visit X} - \text{Baseline}) / \text{Baseline}] * 100$

Days from Surgery

Days from surgery will be calculated as: (Date of the event – Date of surgery)

AE duration

End date of AE – Start date of AE + 1

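### AE and SSI percentages have no time base, although follow-up may run from about 2.75 to 5.25 years; a follow-up summary and an exposure-based rate should stand beside them

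*SAP*

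**What the plan says.** **Accrual.** SAP 6.3 says that "AEs from time of exposure to the study model IOL to the prospective study visit are considered". Each eye therefore has its own observation time, set by its implant date and the date of Visit 1.

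**Eligible exposure.** Protocol 6.4.4, criterion 3, admits subjects implanted for 3 to 5 years, "including implantation up to 90 days before the 3-year timepoint and up to 90 days after the 5-year timepoint". SAP 10.5 applies no analysis windows: a visit outside the window is logged as a deviation but still analysed as Visit 1.

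**Summary measure.** In SAP 6.3.1.1, "the number and percentage of all AEs will be tabulated by Preferred Term (PT) for ocular AEs". For the ocular overview, "the table will report the number of eyes experiencing an AE and the number of adverse events for all eyes by toricity". SSIs get counts and percentages of eyes, for first, second and all eyes by toricity. Under SAP 10.1 the denominators are the analysis set or those assessed, not eye-years.

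**Strata.** SAP 3.2 and 10.4 stratify by toricity and, in eye-level tables, by first and second eye. Follow-up length is not a stratum.

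**Timing information.** The AE and device-deficiency listings carry days from surgery. SAP 10.2 defines it ("Days from surgery will be calculated as" event date minus surgery date). SAP Section 4 sets out disposition, demographic, surgical and biometric summaries, but none of time since implantation.

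**Intended use.** Protocol 6.4.1 and SAP 9 call the descriptive results "sufficient to provide a comparison to shorter term follow-up data of these models, and SotA safety and performance thresholds".

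**The concern.** A percentage of eyes with an event is readable when all eyes were watched for the same time, or when the event can only happen early. Neither is assured here. For an event that keeps accruing, the percentage rises with follow-up, so it reflects both the risk and the implant dates of the subjects who were enrolled.

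Three readings are affected. Set against shorter-term data, a higher long-term percentage may reflect longer observation alone, which can count against the device. Set against a State of the Art threshold, the figure belongs to no stated time point. In the toric/non-toric display, the two groups are filled by model and not matched on implant date, so their follow-up may differ, and no planned table would show whether it does. The listings date the events that occurred but say nothing about how long event-free eyes were followed.

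**Working it through.** **The plan's own figure.** The documents give no safety precision, event rate or event timing. The only precision figure concerns mean binocular BCDVA (SD 0.07 logMAR, n = 100; Protocol 6.4.1, SAP 9): t(0.975, 99) × 0.07/√100 = 0.0139, which agrees with the stated 0.014. It does not bear on safety.

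**Exposure range** (Protocol 6.4.4):
- shortest: 3 − 90/365.25 = 2.754 years
- longest: 5 + 90/365.25 = 5.246 years
- ratio: 5.246/2.754 = 1.91

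Visits outside the window are retained, so the realised range may be wider.

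**Constant hazard (assumption).** The expected percentage of eyes with an event by time T is 1 − exp(−hT).

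| h per 100 eye-years | T = 2.754 | T = 5.246 | Ratio |
|---|---|---|---|
| 0.5 | 1.37% | 2.59% | 1.89 |
| 1 | 2.72% | 5.11% | 1.88 |
| 2 | 5.36% | 9.96% | 1.86 |
| 3 | 7.93% | 14.56% | 1.84 |

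These rows contrast the extremes of individual follow-up, not two groups.

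**A difference in group mix (assumption).** At 1 per 100 eye-years the percentage is 2.96% at 3 years and 4.88% at 5 years.
- 75% of eyes at 3 years, 25% at 5 years (mean 3.5): 0.75 × 2.96 + 0.25 × 4.88 = 3.44%
- the reverse mix (mean 4.5): 0.25 × 2.96 + 0.75 × 4.88 = 4.40%

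The underlying rate is identical in both. Nothing in the documents says that the toric and non-toric groups differ in this way.

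**Early clustering (assumption).** Let 4% of eyes have had an event by 4 years. A share s of those events falls in the first 6 months and the rest is spread evenly after that: F(T) = 4% × [s + (1 − s)(T − 0.5)/3.5].

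| s | T = 2.754 | T = 5.246 | Ratio |
|---|---|---|---|
| 0 | 2.58% | 5.42% | 2.11 |
| 0.5 | 3.29% | 4.71% | 1.43 |
| 0.9 | 3.86% | 4.14% | 1.07 |
| 1 | 4.00% | 4.00% | 1.00 |

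When s = 1 the crude percentage is the stable figure and the rate is not: 4/2.754 ≈ 1.5 against 4/5.246 ≈ 0.8 per 100 eye-years. That is why the rate should be added and the percentage kept.

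**Sampling error.** Take 100 subjects as roughly 200 eyes, treated as independent. At 4% the 95% margin is 1.96 × √(0.04 × 0.96/200) = 2.7 points. For 3.4% against 4.4% with 200 eyes each, the margin on the difference is 1.96 × √(0.034 × 0.966/200 + 0.044 × 0.956/200) = 3.8 points, larger than the 1.0-point shift from mix.

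**Eyes beyond 5 years.** If follow-up were uniform over the window (assumption), the share is (90/365.25)/(5.246 − 2.754) ≈ 10%, or about 10 of 100 subjects.

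**The case against.** The study is descriptive: there are no hypotheses, and toricity is a display stratum with no planned test. The percentage with an event by a visit at 3 to 5 years does answer the objective as written. If the State of the Art thresholds are percentages, the crude percentage is the figure to compare; they sit in a source that is not public. Part of the SAP is also missing from the public text, including Section 6.1 and the output shells cited as Section 14.2, so a follow-up summary there cannot be ruled out.

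Much of this stands. No planned inference is made invalid, and the crude figures should stay. But being descriptive does not answer the point, because the plan itself intends a comparison with data of a different duration, and that comparison needs a time base.

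A reader might infer more than the documents support:
- **That reported safety figures will be off by a factor of about 1.9.** That is the ratio of extreme individual follow-up times under constant hazard. Event timing is not given, and early clustering removes most of the effect.
- **That the toric/non-toric display is biased.** No imbalance in follow-up is documented, and a modest one would lie within sampling error.
- **That device deficiencies share the problem.** Most examples in Protocol 9.1, such as a broken optic or haptic, unsealed packaging or incorrect power, arise at or before implantation. Lack of performance may arise later.
- **That a 5-year cumulative incidence is needed.** Few eyes may be at risk at that point.

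Nor would a rate cure selection. All subjects must attend Visit 1, and exclusion 3 removes those who had an exchange after the 3-year minimum and no longer have a study IOL.

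**Conclusion.** The concern holds for AEs and SSIs that arise after the perioperative period. Their percentages will depend on the follow-up mix, and the SAP text available gives the reader no means of judging by how much. The size cannot be fixed from the documents. Under constant hazards of 0.5 to 3 per 100 eye-years, the percentage at the longest eligible exposure is 1.84 to 1.89 times that at the shortest; the ratio falls to 1.07 if 90% of events come in the first 6 months, and to 1.00 if all do. The issue is one of interpretation and comparability, not of error rates, and it is a worthwhile, inexpensive improvement rather than a defect that undermines the study.

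**What to change.** In SAP 6.3.1.1, keep the crude n (%) and add, by toricity:

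1. The distribution of time from implantation to Visit 1, with total eye-years (subject-years for non-ocular AEs).
2. For ocular AEs, SAEs, ADEs, the named primary safety events and SSIs: the number of eyes with a first event per 100 eye-years. Exposure should end at the first event or Visit 1, whichever is earlier. Give a 95% CI that allows for two eyes per subject, for example by clustering on subject.

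Cumulative incidence at 3 years is an optional addition. A 5-year estimate is not recommended, and SAP 6.3.1.2 on device deficiencies can stay as it is.

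State beside the tables that all figures are conditional on attending Visit 1 still implanted with a study IOL, and that onset is uncertain for conditions first detected at Visit 1.

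**Cost.** SAP wording and a few extra table columns. Surgery and event dates are already needed for days from surgery. SAP 6.3 says which events with partial dates are counted but not where to place them in time, so a short rule for that is needed.
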